9.10.2 Secondary Efficacy Endpoints

The secondary efficacy endpoints include the following variables.

1) Proportion of patients positive for virus titer and proportion of patients positive by RT-PCR at each time point

Defined as the percentage of patients whose virus titer is not < the lower limit of quantification among those assessed for virus titer, and the percentage of patients with detectable virus RNA among assessed by RT-PCR, respectively.

2) Change from baseline in virus titer and in the amount of virus (RT-PCR) at each time point

Defined as the change from baseline in virus titer and the change from baseline in the amount of virus RNA, respectively. Baseline is defined as the last value obtained before the initial dose.

3) AUC adjusted by baseline in virus titer and in the amount of virus RNA (RT-PCR)

Defined as AUC, where AUC is the area under the curve, of change from baseline in virus titer and AUC of change from baseline in the amount of virus RNA, respectively. AUC is calculated using the trapezoidal method.

4) Time to cessation of viral shedding by virus titer and by RT-PCR

Defined as the time between the initiation of the study treatment and first time when the virus titer is < the lower limit of quantification and the time between the initiation of the study treatment and first time when virus RNA by RT-PCR is < the lower limit of quantification, respectively.

5) Proportion of patients whose symptoms has been alleviated at each time point

Defined as the percentage of patients whose primary endpoints are improved after the initiation of the study treatment in the analysis population by each time point. 6) Time to alleviation of symptoms (cough, sore throat, headache, nasal congestion, feverishness or chills, muscle or joint pain, and fatigue)

Defined as the time between the initiation of the study treatment and the alleviation of influenza symptoms. The alleviation of influenza symptoms is defined as the time when all of 7 influenza symptoms have been assessed by the patient as 0 (None) or 1 (Mild) in the patient eDiary, for a duration of at least 21.5 hours (24 hours -10%).

7) Time to improvement in the 4 systemic symptoms (headache, feverishness or chills, muscle/joint pain, and fatigue)

Defined as the time between the initiation of the study treatment and the improvement in the 4 systemic symptoms. The assessment follows the criteria for the primary endpoint.

8) Time to improvement in the 3 respiratory symptoms (cough, nasal congestion, and sore throat)

Defined as the time between the initiation of the study treatment and the improvement in the 3 respiratory symptoms. The assessment follows the criteria for the primary endpoint.

9) Time to resolution of fever

Defined as the time between the initiation of the study treatment and the resolution of fever. The resolution of fever is defined as the time when the patient's self-measured temperature becomes $< 37^{\circ}$ C and is maintained at $< 37^{\circ}$ C for a duration of at least 12 hours.

10) Proportion of patients reporting normal temperature at each time point

Defined as the percentage of patients whose temperature resolves to $< 37^{\circ}$ C after the initiation of the study treatment in the analysis population.

11) Body temperature at each time point

Defined as measured axillary temperature.

12) Time to improvement of each influenza symptom

Defined as the time between the initiation of the study treatment and the alleviation of each influenza symptom. The alleviation of a symptom is defined as the time when the symptom is assessed as 0 (None) or 1 (Mild), for a duration of at least 21.5 hours (24 hours -10%).

13) Time to return to preinfluenza health status

Patients will be asked to record their preinfluenza health status between 0 (worst possible health) and 10 (normal health [for someone your age and your health condition]). Return to preinfluenza health status is defined as time from the initiation of the study treatment to time to the same number on scale for preinfluenza health status.

14) Requirement for systemic antibiotics for infections secondary to influenza infection

Defined as the percentage of patients treated with systemic antibiotics.

15) Incidence of influenza-related complications (hospitalization, death, sinusitis, bronchitis, otitis media, and radiologically confirmed pneumonia)

Defined as the percentage of patients in the analysis population who experience each influenza-related complication (hospitalization, death, sinusitis, otitis media, bronchitis, and radiologically-confirmed pneumonia) as an adverse event after the initiation of the study treatment. A specific complication eCRF with diagnostic criteria for the complications of sinusitis, otitis media, bronchitis, and pneumonia will be provided.

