4.2 Inclusion Criteria

Patients who fulfill all of the following criteria will be included in the study:

- 1. Patients or their legal guardians who provide written informed consent to participate in the study on a voluntary basis. For adolescent patients, informed consent/assent of voluntary participation should be obtained in accordance with local requirements (see Section 7.1).
- 2. Male or female patients ≥ 12 years at the time of signing the informed consent/assent form.
- 3. Patients with a duration of influenza symptoms confirmed by all of the following:
 - a. Fever \geq 38°C (axillary) during the predose examinations or within the 4 hours prior if antipyretics were taken
 - b. At least 1 each of the following general and respiratory symptoms associated with influenza (excluding those that are chronic and existed in the 30 days prior to the influenza episode) is present with a severity of moderate or greater:
 - i. General symptoms (headache, feverishness or chills, muscle or joint pain, or fatigue)
 - ii. Respiratory symptoms (cough, sore throat, or nasal congestion)
- 4. The time interval between the onset of symptoms and the predose examinations (Screening) is 48 hours or less. The onset of symptoms is defined as either:
 - a. Time of the first increase in body temperature (an increase of at least 1°C from normal body temperature)
 - b. Time when the patient experiences at least 1 new general or respiratory symptom
- 5. If a women of childbearing potential (WOCBP), agrees to use a highly effective method of contraception for 3 months after the first dose of S-033188 or oseltamivir (see Section 6.3.1 for approved contraceptive requirements).
- 6. Patients will be considered at high risk* of influenza complications due to the presence of at least 1 of the following inclusion criteria:

- a. Asthma or chronic lung disease (such as chronic obstructive pulmonary disease [COPD] or cystic fibrosis)
- b. Endocrine disorders (including diabetes mellitus)
- c. Residents of long-term care facilities (eg, nursing homes)
- d. Compromised immune system (including patients receiving corticosteroids not exceeding 20 mg of prednisolone or equivalent, and patients being treated for human immunodeficiency virus (HIV) infection with a CD4 count > 350 cells/mm³ within the last 6 months)

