The required sample size will therefore be calculated based on the conservative assumption of a 36-hour difference (assuming that the median time to improvement of influenza symptoms in the placebo group and the S-033188 group was 150 and 114 hours, respectively) in the median time to improvement of influenza symptoms between the S-033188 group and the placebo group to ensure at least 90% power in the efficacy evaluation of S-033188.

Patients will be randomized on a 1:1 basis to either S-033188 or placebo and a follow-up period will be 336 hours (14 days). Assuming that the time follows an exponential distribution, the study will require 790 patients in the ITTI population in order for the generalized Wilcoxon test to have 90% or more power with a 2-sided significance level of 5% (395 patients in the S-033188 group and placebo group, respectively).

Using a 1:1 randomization ratio between the S-033188 group and the oseltamivir group, the ITTI population of oseltamivir will be 395 patients. Table 9-1 shows the statistical power to compare between the S-033188 group and the oseltamivir group under several sets of assumed time to improvement of influenza symptoms.

Table 9-1	Statistical Power to Compare Between S-033188 and
	Oseltamivir

Median Time to Alleviation of Symptoms (S-033188, Oseltamivir)	Statistical Power for Comparison Between S-033188 and Oseltamivir by Generalized Wilcoxon Test
(114 hours, 126 hours)	22.3%
(108 hours, 126 hours)	45.3%
(102 hours, 126 hours)	71.5%
(96 hours, 126 hours)	90.2%

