9.10.3.2 Analyses of Secondary Endpoints

1) Proportion of patients positive for influenza virus titer and proportion of patients positive by RT-PCR at each time point

Only patients whose virus titer/RT-PCR predose at Visit 1 are \geq the lower limit of quantification will be included in the analyses. The summary table by each time

point will be made. The Mantel-Haenszel test at each time point will be used to compare the proportion of patients with positive virus titer/RT-PCR between S-033188 and oseltamivir/placebo with baseline symptom score ($\leq 14, \geq 15$), preexisting and worsened symptom (Yes, No), and region (Asia, North America/Europe, Southern Hemisphere) as stratification factors.

2) Change from baseline in virus titer and the amount of virus RNA (RT-PCR) at each time point

Only patients whose virus titer/RT-PCR predose at Visit 1 are \geq the lower limit of quantification will be included in the analyses. The van Elteren test will be used by each time point to compare the S-033188 with oseltamivir/placebo, where baseline symptom score ($\leq 14, \geq 15$), preexisting and worsened symptom (Yes, No), region (Asia, North America/Europe, Southern Hemisphere) will be included as stratification factors. Summary statistics will be calculated by time point and by treatment group.

3) AUC adjusted by baseline in virus titer and in the amount of virus RNA (RT-PCR)

Only patients whose virus titer/RT-PCR predose at Visit 1 are \geq the lower limit of quantification will be included in the analyses. The same statistical methods as 2) change from baseline in virus titer and the amount of virus RNA (RT-PCR) at each time point will be used. Summary statistics will be calculated by treatment group.

4) Time to cessation of viral shedding by virus titer and by RT-PCR

Only patients whose virus titer/RT-PCR predose at Visit 1 are \geq the lower limit of quantification will be included in the analyses. The same analyses as the primary endpoint will be performed.

5) Proportion of patients whose symptoms has been alleviated at each time point

The same analyses as 1) proportion of patients positive for influenza virus titer and proportion of patients positive by RT-PCR will be used.

6) Time to alleviation of symptoms

The same analyses as the primary endpoint will be performed.

 Time to improvement in the 4 systemic symptoms (headache, feverishness or chills, muscle/joint pain, and fatigue)

The same analyses as the primary endpoint will be performed.

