8) Time to improvement in the 3 respiratory symptoms (cough, nasal congestion, and sore throat)

The same analyses as the primary endpoint will be performed.

9) Time to resolution of fever

The same analyses as the primary endpoint will be performed.

10) Proportion of patients reporting normal temperature at each time point

The summary table by each time point will be made. The Mantel-Haenszel test at each time point will be used to compare the proportion of resolution of fever between S-033188 and oseltamivir/placebo with baseline symptom score (≤ 14 , ≥ 15), preexisting and worsened symptom (Yes, No), and region (Asia, North America/Europe, Southern Hemisphere) as stratification factors.

11) Body temperature at each time point

The summary table by each time point will be made. The analysis of covariance (ANCOVA) will be used by each time point to compare body temperature between S-033188 and oseltamivir/placebo, where composite symptoms score at baseline, and preexisting and worsened symptom (Yes, No), and region (Asia, North America/Europe, Southern Hemisphere) will be used as covariates.

12) Time to improvement of each influenza symptom

The same analyses as the primary endpoint will be done. Patients whose symptoms at baseline are assessed as 0 (None), 1 (Mild), 2 (Moderate) but preexisting and not worsened, or 3 (severe) but preexisting and not worsened will be excluded from the analysis.

13) Time to return to preinfluenza health status

The same analyses as the primary endpoint will be performed.

14) Requirement for systemic antibiotics for infections secondary to influenza infection

A summary table will be created. The Fisher's exact test will be used to compare the percentage of patients who used systemic antibiotics for infections secondary to influenza infection between S-033188 and oseltamivir/placebo.

15) Incidence of influenza-related complications (hospitalization, death, sinusitis, bronchitis, otitis media, and radiologically-confirmed pneumonia)

A summary table will be created. Fisher's exact test will be used to compare the incidence between S-033188 and oseltamivir/placebo.

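### Time to resolution of fever has no baseline-temperature condition, so patients already below 37°C before dosing can count as early resolutions in every arm and dilute the comparison.

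*Protocol*

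**What the plan says.** - **Endpoint (Protocol 9.10.2, item 9).** "The resolution of fever is defined as the time when the patient's self-measured temperature becomes" less than 37°C, held for at least 12 hours. Time runs from the start of study treatment.
- **Analysis (9.10.3.2, item 9).** "The same analyses as the primary endpoint will be performed". Section 9.10 makes the ITTI the main efficacy population. Item 9 has no baseline-temperature condition.
- **Entry (4.2, criterion 3a).** Fever of 38°C or more at the predose examinations, or "within the 4 hours prior if antipyretics were taken". The Synopsis words the antipyretic clause differently: there the fever must be present more than 4 hours after the antipyretic.
- **Other endpoints in 9.10.3.2.** Items 1 to 4 carry a baseline condition ("Only patients whose virus titer/RT-PCR predose at Visit 1 are" at or above the limit of quantification). Item 12 excludes patients with nothing to improve in that symptom ("Patients whose symptoms at baseline are assessed as 0 (None), 1 (Mild), 2 (Moderate) but preexisting and not worsened", and the corresponding severe category).
- **Readings (7.4.1.1).** Temperature is taken four times daily to Day 3, then twice daily. After treatment starts, readings come before acetaminophen or more than 4 hours after it. A study-centre temperature taken on Day 1 before consent may stand in for the predose value.

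**The concern.** Under Section 4.2 a patient can qualify on a fever measured before an antipyretic took hold and be below 37°C when dosed. If the temperature then stays below 37°C for 12 hours, the patient is scored as resolved at the first postdose readings whichever arm was assigned. Such an event says nothing about treatment. It falls where the generalized Wilcoxon test gives most weight, because that test weights each event by the number still at risk. The fever curves are pulled together, so the median difference and the power for this endpoint are understated. Baseline conditions in items 1 to 4 and 12 deal with the same problem; item 9 has none.

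**Working it through.** **Inputs from the protocol (9.2).** "generalized Wilcoxon test to have 90% or more power with a 2-sided significance level of 5" per cent; medians for placebo and S-033188 that "was 150 and 114 hours, respectively"; exponential times; 336 hours of follow-up; 395 ITTI patients per arm. These concern the primary endpoint. No power is stated for fever.

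**Inputs not in the protocol.** The share *f* of each arm that is below 37°C predose and stays there, and the fever medians. Both are assumed and varied.

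**1. The plan's own figure.** Let λᵢ = ln 2 / medianᵢ, yᵢ = ½·exp(−λᵢt) and W = y₁ + y₂. Then

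μ = √(2n) · |∫ W·y₁y₂/(y₁+y₂)·(λ₁−λ₂) dt| / √(∫ W²·y₁y₂/(y₁+y₂)²·(y₁λ₁+y₂λ₂) dt), integrated from 0 to 336 h, and power = Φ(μ − 1.960).

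With n = 395 and medians 114 and 150 h, μ = 3.242 and power is 90.01%; 395 is the smallest n per arm that reaches 90%. Table 9-1 is also reproduced: 22.2, 45.3, 71.5 and 90.2% against the printed 22.3, 45.3, 71.5 and 90.2%. The method therefore matches the plan's.

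**2. Adding a share *f* with an immediate event in both arms.**

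- *Kept.* The risk set and the weight after the first readings both shrink by (1−f), so the signal shrinks by (1−f)². The variance becomes (1−f)³·v₀ + f(1−f)/4, with v₀ close to 1/12 when little is censored. Hence μ is multiplied by (1−f)^1.5 / √((1−f)² + 3f).
- *Excluded.* Only n falls, so μ is multiplied by √(1−f).

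For f = 10%, kept: 0.854/1.054 = 0.810; 3.242 × 0.810 = 2.63; Φ(0.67) = 75%. Excluded: 3.242 × 0.949 = 3.08; Φ(1.12) = 87%.

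Simulation used 3,000 trials per setting, with the uninformative event at 4 h:

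| f | Kept, formula | Kept, simulated | Excluded, formula | Excluded, simulated |
|---|---|---|---|---|
| 5% | 83% | 83% | 88.5% | 89% |
| 10% | 75% | 76% | 87% | 87% |
| 20% | 55% | 56% | 83% | 83% |
| 30% | 36% | 40% | 77% | 77% |

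**3. Other assumed fever effects (simulated, f = 5, 10, 20, 30%).**

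- Medians 32 and 42 h: kept 85, 78, 63, 46%; excluded 88, 88, 83, 79%.
- Medians 25 and 42 h: kept 100, 100, 99, 93%; excluded about 100% throughout.

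**4. When only some stay below 37°C.** Suppose 20% are below predose but only 5% stay there, and the other 15% behave like everyone else. Keeping all is the 5% row, 83%. Excluding all 20% is the 20% row, 83%. With an assumed placebo median of 48 h, a ratio of 114/150 = 0.76, and readings every 6 then 12 h, the pair is 86% kept and 85% excluded. Here the restriction gains no power.

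**5. Medians.** If a share f resolves at once and the rest are exponential, the median solves (1−f)·exp(−λt) = ½. Each median, and so their difference, is multiplied by ln(2(1−f))/ln 2: 0.93, 0.85 and 0.68 for f = 5, 10 and 20%. A 10 h difference (42 minus 32 h) would show as 9.3, 8.5 and 6.8 h.

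**6. Type I error.** The early events follow the same law in all arms, so the test keeps its level. The effect is conservative only.

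**The case against.** Several points on the other side stand.

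- A reader might infer that item 9 is the one endpoint without a baseline condition. It is not: item 10 (normal temperature at each time point) and item 13 (return to preinfluenza health) have none either.
- A reader might infer that every patient below 37°C predose is scored as resolved at once. The 12-hour condition prevents this: a patient whose fever returns as the antipyretic wears off contributes an informative time. The screen is partial, since under Table 7-1 a bedtime reading and the next morning's can span 12 hours, and the 4-hour timing rule names only acetaminophen.
- The Synopsis wording of criterion 3a would largely close the entry route. It conflicts with Section 4.2, and the document does not show which governs.
- These patients had 38°C or more shortly before, so the parallel with an unquantifiable virus titre is imperfect.
- The verb in item 9 could be read as requiring an earlier reading at or above 37°C. That reading would leave patients who never reach 37°C after dosing without a defined outcome, so it does not settle their handling.
- The endpoint is secondary and outside the stated type I error hierarchy. The full ITTI is a defensible set, and a SAP not at hand may restrict it.

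None of this alters the text: Section 9.10.3.2 fixes analysis sets endpoint by endpoint and gives item 9 no condition.

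**Conclusion.** The point holds as a correctable weakness in one secondary endpoint. As written, item 9 can count patients who were already below 37°C at dosing as early resolutions, which understates the fever difference and its power.

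The documents do not support a specific power loss. The figures above rest on an assumed share f, exponential times and borrowed or assumed effects. They run from a fall of roughly 7 points at f = 5% (90% to 83%), or 34 points at f = 20% (90% to 56%), at the 114 versus 150 h effect, to almost nothing with 25 versus 42 h. Nor do they support the claim that exclusion always gains power: that depends on how many of those below 37°C stay there. The primary analysis, the sample size and the type I error are not affected.

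**What to change.** 1. In 9.10.3.2 item 9, limit the analysis to patients at or above 37°C at the last temperature reading before the first dose. Name that reading explicitly: Section 7.4.1.1 lets a pre-consent site temperature serve as the predose value, and this could be the reading taken before the antipyretic acted. State how patients with only a pre-consent reading are classified.
2. Report the number excluded per arm, and show the all-ITTI result as a sensitivity analysis.
3. Reconcile the antipyretic clause of criterion 3a between the Synopsis and Section 4.2.

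The restriction uses a baseline value, so it keeps the randomised comparison, provided that it is fixed before unblinding. It takes a few sentences in the protocol or SAP and, for most patients, no new data. The price is a smaller set for this endpoint, which also drops some patients whose fever returns and who would have been informative.

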7.9 Appropriateness of Measurements

7.9.1 Primary Efficacy Endpoint

The time to improvement of symptoms is defined as the time to improvement of 7 influenza symptoms (cough, sore throat, headache, nasal congestion, feverishness or chills, muscle or joint pain, and fatigue). The time to alleviation of symptoms has been commonly used as a measure of the efficacy of anti-influenza virus drugs, thereby enabling a comparison with the results from clinical studies of currently available medications. Since some "high risk" individuals may have underlying chronic diseases that share some symptoms with those of influenza (ie, cough in a patient with chronic lung disease), a modification of time to alleviation has been included in this protocol to permit improvement of a symptom that may have been present before the onset of influenza but worsened by influenza, or maintenance of a preexisting symptom that has not been worsened by the onset of acute influenza. This is a novel and untested endpoint but is considered by the sponsor to be a reasonable approach to avoid confounding of results due to persistent preexisting symptoms that cannot be completely alleviated.

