9.10.1 Primary Efficacy Endpoint Analyses

The primary efficacy endpoint will be the time to improvement of influenza symptoms (with modification for preexisting symptoms):

- Preexisting symptoms (ie, cough, fatigue, or muscle/joint pain that existed prior to developing influenza) that were judged by the patient to be worse at baseline (ie, the predose examinations) must improve from baseline severity
 - o Improvement in baseline severity is as follows:
 - Severe \rightarrow moderate, mild, or absent
 - Moderate \rightarrow mild or absent
 - Note: At baseline (ie, the predose examinations), patients will only be asked if
 preexisting symptoms existed (within the last 30 days) and if they were
 worsened by influenza. Patients will be asked to rate the severity at baseline
 that is the severity that needs to improve. To avoid recall bias, patients will
 not be asked to rate the severity of preexisting symptoms prior to influenza.
- Preexisting symptoms (ie, cough, fatigue, or muscle/joint pain that existed prior to developing influenza) that were judged by the patient to NOT be worse at baseline (ie, the predose examinations) must have their baseline severity maintained

- o Maintenance of baseline severity is as follows:
 - Severe \rightarrow Severe
 - Moderate \rightarrow Moderate
- For new symptoms at baseline (ie, the predose examinations), alleviation of symptoms assessment will not be modified
 - Alleviation of symptoms is as follows:
 - Severe \rightarrow mild or absent
 - Moderate \rightarrow mild or absent

Once all of a patient's influenza symptoms are alleviated, maintained, or improved as defined above, the endpoint for that patient will be reached, for a duration of at least 21.5 hours (24 hours – 10%).

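### Protocol item 12, the time to improvement of each symptom, is scored as alleviation to none or mild, so it departs from the primary endpoint's rule when a preexisting, worsened symptom goes from Severe to Moderate

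*Protocol*

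**What the plan says.** Four parts of the protocol bear on this.

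- **Primary endpoint (Section 9.10.1).** Preexisting cough, fatigue or muscle/joint pain that the patient judged worse at baseline "must improve from baseline severity". The listed steps accept Severe to moderate, mild or absent, and Moderate to mild or absent. For symptoms new at baseline, "alleviation of symptoms assessment will not be modified": they must reach mild or absent.
- **Items 7 and 8 (Section 9.10.2).** The improvement endpoints for the four systemic and the three respiratory symptoms each carry the sentence "The assessment follows the criteria for the primary endpoint".
- **Item 12 (Section 9.10.2).** The title speaks of improvement of each symptom, but the text reads "Defined as the time between the initiation of the study treatment and the alleviation of each influenza symptom". It continues: "The alleviation of a symptom is defined as the time when the symptom is assessed as 0 (None) or 1 (Mild"), for at least 21.5 hours. Neither a modification for preexisting symptoms nor the sentence used in items 7 and 8 appears.
- **Analysis of item 12 (Section 9.10.3.2).** The exclusions begin "Patients whose symptoms at baseline are assessed as 0 (None), 1 (Mild), 2 (Moderate) but preexisting and not worsened" and end with "2 (Moderate) but preexisting and not worsened, or 3 (severe) but preexisting and not worsened will be excluded from the analysis". Preexisting symptoms that were worsened and are moderate or severe at baseline are not excluded.

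Section 7.9.1 gives the reason for modifying the primary endpoint: to "avoid confounding of results due to persistent preexisting symptoms that cannot be completely alleviated".

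**The concern.** Item 12 shares the improvement label with the primary endpoint and items 7 and 8 but uses the event rule of item 6, the unmodified alleviation endpoint. Its exclusions show that preexisting status was considered, yet they deal only with the symptoms that influenza did not worsen. The worsened ones are kept and held to the threshold that the modification was designed to relax.

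Two things are at stake. The first is consistency: the same cough can count as improved in the primary endpoint and item 8 while item 12 records no event at that time. A reader who sets the symptom-level results beside the composite would take the two to use one definition. The second is sensitivity. Chronic symptoms that settle at a moderate level enter the single-symptom comparisons as late events or as censored times. This can happen in every arm and would tend to blur the treatment contrast for cough, fatigue and muscle or joint pain, the three symptoms for which the modification was written.

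**Working it through.** No stated figure in the protocol depends on this definition, so there is none to reproduce. The check is to score every possible transition under both rules.

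**Inputs.** Severity is rated 0 None, 1 Mild, 2 Moderate, 3 Severe (Section 7.4.1.2). Let b be the baseline score and t a follow-up score that is held for at least 21.5 hours.

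- Primary rule, new symptom (9.10.1): event if t ≤ 1.
- Primary rule, preexisting and worsened (9.10.1): event if t < b.
- Item 12 rule (9.10.2): event if t ≤ 1, whatever the history of the symptom.
- Item 12 exclusions (9.10.3.2): b = 0, b = 1, and any preexisting symptom that was not worsened.

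**Retained transitions.** 2 histories (new; preexisting and worsened) × 2 baseline levels (Moderate, Severe) × 4 follow-up levels = 16.

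| History | Baseline | Follow-up | Primary rule | Item 12 |
|---|---|---|---|---|
| New | Moderate | None, Mild | event | event |
| New | Moderate | Moderate, Severe | no | no |
| New | Severe | None, Mild | event | event |
| New | Severe | Moderate, Severe | no | no |
| Preexisting, worsened | Moderate | None, Mild | event | event |
| Preexisting, worsened | Moderate | Moderate, Severe | no | no |
| Preexisting, worsened | Severe | None, Mild | event | event |
| Preexisting, worsened | Severe | **Moderate** | **event** | **no** |
| Preexisting, worsened | Severe | Severe | no | no |

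**Result.** 15 of 16 agree and 1 of 16 differs. These are counts of possible transitions, not shares of patients. For worsened symptoms that are Moderate at baseline, the condition t < 2 is the same as t ≤ 1, so the rules coincide.

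**Which analyses.** Section 9.10.1 limits preexisting symptoms to cough, fatigue and muscle/joint pain, so 3 of the 7 single-symptom analyses can be affected. Cough is also part of item 8; fatigue and muscle/joint pain are part of item 7.

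**What happens to an affected symptom.** Take, as an illustration, a preexisting, worsened cough that is Severe at baseline and holds at Moderate from Day 4. The primary endpoint and item 8 treat this symptom as improved from Day 4.

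- If it then holds at Mild from Day 6, item 12 records an event at Day 6: two days later, but still an event.
- If it stays Moderate through the Day 14 diary, item 12 has no event and the time is censored.

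**After the change.** If item 12 used the primary criteria, the one discordant row would become an event and no other row would change.

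**The case against.** **The analysis section already brings in the primary rule.** Section 9.10.3.2 says that item 12 is analysed as the primary endpoint is. But that section describes statistical analyses, and it applies the same instruction to viral shedding and to resolution of fever, where the symptom rule cannot apply. The event definition remains the explicit 0/1 rule of Section 9.10.2.

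**The wording is loose throughout.** Item 5 speaks of alleviation while using the primary criteria. That is so, but item 12 fixes numeric scores, and loose wording does not change those.

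**The SAP can settle it.** Section 9.1 has the SAP follow this section and explain any deviation. The protocol does not leave the definition open; it states one.

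**The threshold may be deliberate.** Section 7.9.1 calls the modified endpoint novel and untested and describes alleviation as commonly used, and its rationale is written for the primary endpoint alone. Nowhere is item 12 given the task of explaining the composite result. A conventional threshold for single symptoms is therefore defensible. This part stands, and it is why the point concerns consistency and not validity. Yet no such choice is stated, item 6 already supplies the unmodified version for the composite, and the improvement title points the other way.

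**Stratification protects the comparison.** The test is stratified by preexisting and worsened symptom, which is also a randomization factor, so affected patients are compared within their own stratum. This answers a worry about confounding between arms. It does not alter what counts as an event.

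**Stronger readings.** A reader might infer that every chronic symptom counted as improved in the primary endpoint fails in item 12. The table shows that this needs a Severe baseline and a Moderate follow-up. A reader might infer that each such patient is censored at Day 14; that holds only if the symptom never stays at 0 or 1 for 21.5 hours. A reader might also infer from the randomization stratum that many patients are affected. Section 5.4 puts a patient in the Yes category for any one of the three symptoms with no condition on severity, and gives no prevalence. The protocol supports none of these readings.

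**Conclusion.** The inconsistency is real and narrow. Item 12 carries an improvement title with an alleviation rule, and it departs from the primary endpoint and items 7 and 8 at a single transition: Severe to Moderate in preexisting, worsened cough, fatigue or muscle/joint pain. The effect on an affected symptom is a delayed event or, if it never holds at 0 or 1, a censored time.

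The number of patients concerned cannot be derived. The protocol gives no prevalence of preexisting, worsened symptoms that are Severe at baseline, and Section 9.10.1 states that patients are not asked to rate preexisting symptoms as they were before influenza. Any loss of sensitivity is therefore unquantified.

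The hierarchy in Sections 9.1 and 9.10.3.1 covers only the two comparisons of the primary endpoint. Item 12 is one of 15 secondary endpoints outside it, so the primary result, type I error control and sample size are unaffected. The conclusion rests on reading the item 12 definition as written and on reading the reference to the primary analyses as referring to statistical method. The definition should be corrected because it is cheap to align and the present text invites misreading.

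**What to change.** Before unblinding, redefine item 12 in Section 9.10.2 as the time from the start of study treatment to improvement of each influenza symptom, and add the sentence already used in items 7 and 8: "The assessment follows the criteria for the primary endpoint". Keep the 21.5-hour duration, and keep the exclusion of preexisting, not worsened symptoms in Section 9.10.3.2. If the 0/1 version is also wanted, report it separately under the name 'time to alleviation of each symptom'.

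The cost is one sentence in the definition, carried into the SAP, plus one extra set of tables if both versions are reported. No new data are needed: under Section 9.10.1 patients are already asked at baseline whether a symptom was preexisting, whether influenza worsened it, and how severe it is. Making the change before unblinding keeps the choice from looking data-driven.
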